All participant data were obtained and recorded in individual files that was stored in a secured file cabinet within a locked office. Upon study entry, all participants were given a unique identifier to be used through the entirety of the study and this too was maintained in a locked file cabinet in secured office. Following each study visit, the data obtained was entered into a database using the study participants' unique identifiers. All other personal data were omitted from electronic records. At the close of the study, any missing data was verified with chart review. Only authorized study personnel have access to patient data.

Data Analysis

The primary outcome measured was MMP-9 activity. Based on our preliminary data, we expect that n=16 per group would be sufficient to detect a 20% and 25% decrease in MMP-9 activity in the treated group (10mg/kg and 20mg/kg; respectively) relative to placebo with 80% power.

[name] (Professor, UAB School of Public Health) is the biostatistician for this clinical trial.

Nasal and Endotracheal Aspirate Collection and Processing

Nasal samples were collected using a nasal swab inserted through the nares parallel to the palate (not upwards) until resistance was encountered or the distance inserted was equivalent to that from the nostril to the ear of the patient indicating contact with the nasopharynx. After gentle rubbing and rolling of the swab, it was left in place for several seconds to absorb secretions prior to removal. The swab was then immediately placed into a sterile vial containing 3 ml of viral transport media (Quidel, San Diego, CA), and kept at 4°C for further analysis.

Endotracheal aspirates were collected via endotracheal tube suctioning using an 8 Fr suction cannula (CareFusion, San Diego, CA, USA) and centrifuged at 500xg for 10 min to separate supernatant from cells and mucus (pellet) . Separate aliquots of supernatant were subsequently saved at 4°C for further analysis.

Assay of AZM, Urea and Pharmacokinetic Analysis

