This study was designed to have a total sample size of 48 participants divided into three groups, with 16 per group to detect a 25% and 37.5% decrease in lung MMP-9 activity in the treated groups (10mg/kg and 20mg/kg, respectively) relative to placebo with 80% power using analysis of variance. The assumptions were based on MMP-9 levels found in endotracheal aspirate of children with RSV-induced respiratory failure (Kong et al, *ERJ* 2014).

Means, standard deviations, medians, quartiles and range (minimum, maximum) described continuous variables and counts and percentages for categorical variables. To compare baseline characteristics among the treatment groups, we used Kruskal-Wallis test for age, height and weight due to evidence of non-normality of the distribution of the values. We used either Chi-Square or Fisher's exact test for categorical variables depending on expected cell counts.

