We analyzed inflammatory markers by first performing \log_{10} transformation to address the skewness of the distribution and extreme outliers. We then calculated the difference at each time point relative to baseline to obtain the change (i.e. pre and post treatment) outcome and fitted a generalized linear mixed model (GLMM) with random intercepts and assumed unequal variances across treatment groups with change from baseline as the outcome. The model included treatment, day and treatment by day interaction. Point and confidence interval estimates of the mean change outcome at each time point and treatment group combination were obtained. If a confidence interval for the mean change does not include 0, this is evidence of an effect associated with that particular treatment as it is either a significant increase (or decrease) in the inflammatory marker relative to baseline. The Bonferroni approach was used to adjust for multiple testing and simultaneous confidence intervals. Thus, significance was determined using a cut-off of 0.002 and a 99.8% level was used to construct confidence intervals for each for each treatment at each time point. Note that the sample size justification was based on the assumption that the MMP-9 levels are normally distributed with common standard deviation. However, in the data for this trial, we observed evidence of non-normality and non-constant variance across the treatment groups. Thus, GLMM was deemed more appropriate than ANOVA. Furthermore, fitting GLMM allows us to combine unbalanced data from different time points to help gain more power in evaluating treatment effect.

We used a generalized linear model assuming a negative binomial distribution for clinical outcomes (measured in number of days), using log link to address possible overdispersion due to some extreme observations. Furthermore, we fitted a model that allowed the variance to differ by treatment group. Spearman Correlation was used to examine associations. For this set of

analyses, the standard 5% level of significance and 95% confidence interval was used as these are all exploratory outcomes. All analyses were done using SAS version 9.4.

IRB and IND

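### The printed 80% power belongs to an ANOVA on endotracheal MMP-9 that was not the analysis used, is attached to two different effect pairs, and has no counterpart for the log10-change test at the 0.002 cut-off

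*Combined protocol and SAP*

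**What the plan says.** Two sections attach 80% power to the same 16 per arm, with different effects.

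- **Data Analysis:** "n=16 per group would be sufficient to detect a 20% and 25% decrease in MMP-9 activity in the treated group", for 10 mg/kg and 20 mg/kg respectively, relative to placebo. Neither a test nor a sample type is named.
- **Sample Size Determination and Statistical Analysis:** decreases of 25% and 37.5% in lung MMP-9 activity, "relative to placebo with 80% power using analysis of variance". The assumptions are attributed to endotracheal MMP-9 levels from an earlier cohort.

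The latter section then describes a different analysis. Inflammatory markers are put on the log10 scale "to address the skewness of the distribution and extreme outliers". Change from baseline is fitted in a mixed model with variances that differ by arm, and each arm's mean change is judged by a 99.8% interval (cut-off 0.002). It says of the power calculation: "Note that the sample size justification was based on the assumption that the MMP-9 levels are normally distributed with common standard deviation". Of the trial data it says "we observed evidence of non-normality and non-constant variance across the treatment groups". It adds that the mixed model should gain power by combining time points, without a figure.

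Primary and Secondary Outcomes records that the primary MMP-9 outcome changed from endotracheal to nasal when non-ventilated patients were admitted.

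**The concern.** The 80% was computed for one sample type, one scale, one variance assumption and an ANOVA. The MMP-9 result comes from another sample type, another scale, arm-specific variances and a much stricter cut-off. The plan explains why the model changed but does not say what happened to the power. Its only bridging remark suggests an improvement.

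MMP-9 is a primary outcome. A reader who meets a null MMP-9 result may set it against the printed 80% and take it as evidence against reductions of 25% to 37.5%. That inference needs the power of the test performed, which is not given. The two effect pairs add to the problem, because a reader cannot tell which reduction the trial was sized to find.

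**Working it through.** **Inputs from the documents.** Three arms of 16; relative means 1 / 0.75 / 0.625 (Sample Size section) or 1 / 0.80 / 0.75 (Data Analysis); 80% power; ANOVA; analysis cut-off 0.002.

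**Not printed.** The SD and the design alpha. I assume alpha 0.05 for the design. The 80% can therefore only be solved backwards, not reproduced.

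**Formula.** For a one-way ANOVA, λ = n Σ(μᵢ − μ̄)² / σ². Power is the probability that a noncentral F (2 and 45 df, noncentrality λ) exceeds the critical value, 3.204 at alpha 0.05 or 7.158 at 0.002. At 0.05, 80% power needs λ = 10.31.

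**Step 1: SD implied by 80%, as a fraction of the placebo mean.**
- 25%/37.5%: Σ(μᵢ − μ̄)² = 0.0729, so σ = √(16 × 0.0729 / 10.31) = 0.336.
- 20%/25%: Σ(μᵢ − μ̄)² = 0.0350, so σ = √(16 × 0.0350 / 10.31) = 0.233.

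**Step 2: do the two statements agree?** At σ = 0.336 the 20%/25% pair has λ = 16 × 0.0350 / 0.336² ≈ 4.95, hence 47% power. At σ = 0.233 the 25%/37.5% pair has λ ≈ 21.5, hence about 98.5%. Pairwise two-sided t tests (30 df) do not remove the gap. The SDs giving 80% for the low and high dose are 0.244 and 0.366 for one pair, and 0.195 and 0.244 for the other.

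**Step 3: effect of the log10 scale and of the cut-off.** If values are lognormal with CV 0.336, the log10 SD is √ln(1 + 0.336²) / ln 10 = 0.142. The effects become log10(0.75) = −0.125 and log10(0.625) = −0.204, with Σ(μᵢ − μ̄)² = 0.0212. So λ = 16 × 0.0212 / 0.142² ≈ 16.8.
- Alpha 0.05: 95% power.
- Alpha 0.002: about 67%.

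Simulated lognormal data (20,000 runs, alpha 0.05) show the same for scale. Power on the raw and log scales is 94% and 95% at CV 0.337, 65% and 69% at CV 0.5, and 20% and 27% at CV 1.0.

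These figures treat the SD of change as equal to the SD of a single value. The SD of change is SD × √(2(1 − ρ)), so this is exact at a baseline correlation ρ of 0.5. A higher ρ raises power and a lower one reduces it.

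**Step 4: range over assumed SDs of log10 change** (25%/37.5%, omnibus test, one time point).

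| SD of log10 change | Power at 0.05 | Power at 0.002 |
|---|---|---|
| 0.15 | 93% | 59% |
| 0.20 | 71% | 26% |
| 0.30 | 37% | 6.5% |
| 0.50 | 16% | 1.4% |

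80% power needs an SD of 0.181 at alpha 0.05, or 0.128 at 0.002. Under the plan's own rule (each arm's 99.8% interval against zero, one time point, t approximation), power for falls of 25% and 37.5% from baseline is 39% and 93% at SD 0.15, 17% and 64% at 0.20, and 5% and 22% at 0.30. That rule does not test a difference from placebo, which is how the design effects were defined.

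**The case against.** **The plan discloses the mismatch.** It states the design assumptions, reports that the data departed from them, and gives a reason for replacing ANOVA. It never calls 80% the power of the mixed model. This stands, and makes the point an incomplete restatement, not a concealed error. It does not supply the missing figure.

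**A reader might infer that the SD behind the 80% contradicts the reported skewness and outliers.** The documents do not support that. No SD, CV or range is printed. The design values were endotracheal and from another cohort, while the reported distribution is from this trial, whose primary outcome was nasal. The outlier remark covers inflammatory markers collectively. A lognormal with CV 0.337 has skewness of about 1.05, so that SD allows moderate right skew. An SD near 34% of the mean looks optimistic, but that is a question of plausibility.

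**A reader might also infer that the log10 scale itself cost power.** Step 3 shows the opposite at a given CV. The losses at alpha 0.05 in Step 4 come from assuming larger SDs, for which the documents give no evidence.

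**Repeated measures may help.** Combining time points is a standard reason to expect some gain, and the grid uses a single time point. That is fair, but the gain is unquantified and has to be weighed against the 0.002 cut-off.

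**80% could be read as a floor.** At an SD of 0.233 both pairs reach at least 80%. The Sample Size section would then be quoting 80% for about 98.5%, and the text gives no sign of that.

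**Conclusion.** The point holds as a reporting and interpretation problem. The 80% describes an ANOVA on normal, common-SD endotracheal MMP-9 and does not carry over to log10 change in nasal MMP-9 with arm-specific variances at 0.002. No power is given for the latter.

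The two effect pairs need SDs of about 34% and 23% of the placebo mean. At the first of these, the 20%/25% pair has about 47% power. This rests on an omnibus ANOVA at an assumed alpha of 0.05.

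At the SD implied by the 25%/37.5% pair, and assuming lognormal values and ρ = 0.5, omnibus power on the log10 scale is about 95% at 0.05 and about 67% at 0.002. The stricter cut-off, not the scale, lowers it. That the ANOVA was computed on untransformed values is an inference from the wording. No actual power can be stated, because the SD of log10 change is not in the documents.

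**What to change.** 1. Reconcile Data Analysis with the Sample Size section so that one effect pair is given, and state the SD and alpha behind the 80%.
2. Confine the 80% to the design-stage ANOVA on endotracheal MMP-9, and say that it is not the power of the analysis reported.
3. For log10 change in nasal MMP-9 at the cut-off actually used, give the smallest fold-change versus placebo detectable with 80% power. Take the SD from earlier data or show a range. Do not compute post hoc power from the trial's own observed effect.
4. Base the MMP-9 conclusion, including a null one, on the confidence interval for the ratio of each dose to placebo.
5. Qualify the remark about gaining power from the mixed model, noting that the cut-off works the other way.

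The cost is wording and one recalculation, with no extra patients. The stated power will look less favourable.

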Prospective Pilot Clinical Trial of
Azithromycin Treatment in RSV Induced
Respiratory Failure in Children

Study Protocol & Statistical
Analysis Plan

NCT02707523

October 10, 2019

[name]., Principal Investigator
University of Alabama at Birmingham
Birmingham, AL 35294

Study Protocol:

Design

The study was a double-masked, placebo-controlled phase 2 trial with 3 treatment groups (ClinicalTrials.gov NCT02707523). All subjects, their families, medical providers, and study staff were blinded to study medication allocation, with the exception of the biostatistician and the pharmacist.

Recruitment and Enrollment

Subject Recruitment:

16 patients per group [placebo (saline), 10mg/kg azithromycin and 20mg/kg azithromycin group; total=48] were recruited from the Pediatric Intensive Care Unit (PICU) at Children's of Alabama. All children with RSV infection and required positive pressure ventilation (invasive and non-invasive) were screened for eligibility.

Patient Compensation:

None

Race and ethnicity:

The race and ethnicity were classified based on either patient self-identification or by hospital staff during admission. Race and ethnicity were assessed in the study to provide a baseline characterization of patients cared for in this region.

Eligibility/Inclusion Criteria:

Inclusion Criteria:

1. Admission to the PICU at Children's of Alabama with a diagnosis of RSV infection and requiring positive pressure ventilation (invasive and non-invasive). Non-invasive positive pressure ventilation is defined as need for BiPAP (bilevel positive airway pressure) or high flow oxygen (namely, >1 L/kg/min of flow, with a minimum of 5 L/min flow for children <5 kg).
2. Enrollment into the study within 48 hours of ICU admission and placement on positive pressure ventilation
3. Age 0-16 years

Exclusion Criteria:

1. AZM use within 7 days of PICU admission
2. Contraindication to AZM use
 - Patients with electrocardiogram QT interval corrected for heart rate (Qtc) ≥ 450 ms
 - Patients with significant hepatic impairment (direct bilirubin >1.5 mg/dL)
 - Known hypersensitivity to azithromycin, erythromycin, any macrolide, or ketolide drug
 - Cardiac arrhythmia
3. History of pyloric stenosis
4. Patients requiring chemotherapy or on chronic steroids for malignancy or post bone marrow transplantation
5. Positive pressure ventilation greater than 48 hours prior to PICU admission

Informed Consent:

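### The MMP-9 model was chosen after trial data were seen by arm, and its evidence rule makes no comparison with placebo

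*Combined protocol and SAP*

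**What the plan says.** All references are to the combined protocol and SAP.

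- **Sample Size Determination and Statistical Analysis, first paragraph.** The design is "16 per group to detect a 25% and 37.5% decrease in lung MMP-9 activity in the treated groups", "relative to placebo with 80% power using analysis of variance". This is the only place where a design-stage test for MMP-9 is named.
- **Same section, paragraph on inflammatory markers.** Markers are log10-transformed and expressed as change from baseline. They are fitted in a mixed model with random intercepts, arm-specific variances, and terms for treatment, day and their interaction. A confidence interval for an arm's mean change that excludes zero counts as evidence of an effect of that treatment. The cut-off is 0.002, with 99.8% intervals, described as Bonferroni.
- **Same paragraph, reason for the change.** The sample size was "based on the assumption that the MMP-9 levels are normally distributed with common standard deviation", but in the trial data "we observed evidence of non-normality and non-constant variance across the treatment groups". "Thus, GLMM was deemed more appropriate than ANOVA". A further reason follows: the model can combine unbalanced data over time and so gain power.
- **Design.** Everyone was blinded "with the exception of the biostatistician and the pharmacist". Under Randomization, the biostatistician also wrote the allocation schedule.
- **Timing.** The last patient was enrolled in February 2019, and the document is dated October 10, 2019.

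No blinded data review, fallback rule or ANOVA-type sensitivity analysis is described.

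**The concern.** Unequal variance between arms can be seen only in outcome data split by arm. The model for a primary biomarker was therefore settled with arm-level data in view, in a trial whose biostatistician knew the allocation. A nominal significance level is guaranteed only for an analysis fixed in advance, or changed by a rule fixed in advance. Here neither is shown.

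The change also went beyond the reasons given for it. Non-normality is a reason to transform, and unequal variance is a reason to let variances differ by arm. Neither explains moving from a comparison with placebo to a test of each arm against its own baseline. Children recovering from RSV may show a change in MMP-9 in every arm, and a within-arm rule can credit that change to the drug. At stake is whether a reader can attribute an MMP-9 decrease to azithromycin, and whether the finding survives another reasonable model.

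**Working it through.** **1. The plan's own figures**

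Cut-off and interval level agree: 1 − 0.998 = 0.002. A Bonferroni division gives 0.05/25 = 0.002, but neither 25 tests nor a family-wise 0.05 is stated. Biologic Outcome Measurement lists 13 markers. With two post-baseline days, 13 × 2 = 26 and 0.05/26 = 0.0019. With three arms as well, 78 and 0.05/78 = 0.00064. The 0.002 is given only for the log10-change analysis; no alpha is given for the ANOVA.

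The ANOVA sample size cannot be reproduced, because no SD is stated. The text gives only the source: "The assumptions were based on MMP-9 levels found in endotracheal aspirate of children with RSV-induced respiratory failure". Solving backwards, assuming alpha 0.05, with noncentrality λ = n Σ(μᵢ − μ̄)² / CV² and n = 16:
- Decreases of 25% and 37.5%: means 1, 0.75, 0.625; Σ = 0.0729; 16 × 0.0729 = 1.167. Power of 80% needs CV = 0.336 (λ = 1.167/0.113 = 10.3).
- Data Analysis instead calls 16 per group "sufficient to detect a 20% and 25% decrease in MMP-9 activity in the treated group": means 1, 0.80, 0.75; Σ = 0.035; 16 × 0.035 = 0.56. Power of 80% needs CV = 0.233 (λ = 0.56/0.0543 = 10.3).

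Both versions are comparisons between groups. At CV 0.336, the 25%/37.5% ANOVA has 35% power at 0.002.

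**2. What a change of model does to the error rate**

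Simulation with no treatment effect on the log scale, 3 arms of 16, one time point, 20,000 runs. Assumed: the distributions, a Welch ANOVA on log10 values as a stand-in for the mixed model, and a switch from raw ANOVA when a Levene or Jarque-Bera test gives p < 0.05. Rejection rates at nominal 0.002:

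| Data | Keep raw ANOVA | Always Welch on log10 | Switch on diagnostics |
|---|---|---|---|
| Normal, equal SD | 0.0016 | 0.0017 | 0.0016 |
| Normal, SD 1:1:2 | 0.0050 | 0.0019 | 0.0034 |
| Lognormal, equal SD | 0.0010 | 0.0022 | 0.0021 |
| Lognormal, unequal SD | 0.0040 | 0.0022 | 0.0023 |

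The simulation standard error near 0.002 is √(0.002 × 0.998/20,000) = 0.0003. At nominal 0.05, switching on diagnostics gives 0.050 to 0.057.

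A version with repeated measurements (log10 SD 0.5, within-child correlation 0.6, both assumed) switches from raw Day 3 ANOVA to an F test on log10 change when residuals fail a normality test. It gives 4.8% at 0.05 and 0.22% at 0.002. The switch occurs in 99% of runs, because lognormal data almost always fail that test whatever the treatment does.

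**3. What the within-arm rule does**

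Assumed: no treatment effect, a trend d (in SDs of the change) common to all arms, 16 per arm, one day, and a two-sided one-sample t test at 0.002. If p is the chance that one arm is flagged, at least one of the two active arms is flagged with probability 1 − (1 − p)².

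| d | p | 1 − (1 − p)² | Simulated |
|---|---|---|---|
| 0 | 0.002 | 0.004 | 0.004 |
| 0.5 | 0.080 | 0.154 | 0.156 |
| 1.0 | 0.611 | 0.849 | 0.852 |

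Seeing placebo go unflagged does not rescue the rule. The chance that at least one active arm is flagged and placebo is not is 0.144 at d = 0.5 and 0.330 at d = 1.0.

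**The case against.** The departure and its reason are openly disclosed. The stated triggers are distribution and variance, not treatment results, and section 2 of the working shows that such a switch costs little. Where variances differ it can improve error control: with SD 1:1:2, staying with ANOVA gives 0.0050 and the unequal-variance test 0.0019. A mixed model is a sensible choice for unbalanced daily samples, which a one-day Welch test does not handle. All of this stands.

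A reader might go further and infer that the stated error rate has been lost, perhaps to 8% or 10%. Figures of that size (7.8% for the better of two analyses, 10.7% for the best of three, at 0.05) come from running every candidate and keeping the smallest p-value. Nothing in the documents says that this was done, and 0.05 is not the plan's cut-off for these markers. Nor was an ANOVA error rate lost, since none was stated.

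A reader might also infer that the unblinded biostatistician picked the model for its result. The documents do not say who chose it, or whether treatment estimates had been seen. The remark about power comes after the choice has been explained.

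The objection does not answer two points. No rule for the change was fixed in advance, and the evidence rule contains no comparison with placebo. The model's treatment and interaction terms would supply one, but the plan states no such contrast as its test.

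**Conclusion.** The point holds in a limited form. The MMP-9 analysis was chosen after trial data were inspected by arm, without a stated rule and in a trial with an unblinded biostatistician, so the 0.002 level lacks the protection of pre-specification. How much it is inflated, if at all, cannot be determined. If diagnostics alone drove the choice, the simulated level is 0.0016 to 0.0034, under assumed data shapes and with a Welch test in place of the mixed model. Material inflation would need a choice driven by the treatment result, which the documents neither show nor exclude.

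The within-arm rule is the larger weakness for interpretation. With no treatment effect, the chance of flagging an active arm on one day rises from 0.004 to about 0.16 or 0.85 as a common trend goes from 0 to 0.5 or 1.0 SD. The documents give no size for such a trend, so these figures show a range and do not estimate it for this trial.

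**What to change.** - Label the mixed model as chosen after review of the trial data. Say who chose it and whether treatment estimates had been seen by then.
- Beside it, report contrasts of each azithromycin arm with placebo on log10 nasal MMP-9, with confidence intervals, from the mixed model itself and, for example, from a Welch-type ANOVA. Nasal MMP-9 is the current primary measure (Primary and Secondary Outcomes), although the sample size was set for lung MMP-9.
- Call these contrasts supportive. A Welch test on log10 values is not the ANOVA used for the sample size, which assumed normal levels with a common SD.
- State whether the MMP-9 conclusion depends on the model.

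Both analyses need not reach significance. That would be a debatable trade of power in a pilot of 48 children, and the plan gives no power calculation for it.

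The cost is one extra analysis and a few sentences. The downside is that an MMP-9 result seen only in the within-arm intervals must be called exploratory.
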